5.3 Dose Modifications

5.3.1 Pembrolizumab Dose Modifications

Retreatment criteria for pembrolizumab and cisplatin are independent (retreatment criteria for cisplatin are specified in section 5.3.2 below). There are no dose reductions for pembrolizumab. If the subject meets retreatment criteria, the full dose of 200 mg will be administered. If subjects do not meet retreatment criteria, then the dose of pembrolizumab will be SKIPPED. The sole exception to this rule is the first dose of pembrolizumab following completion of chemoradiotherapy, on both Arms 1 and 2. Although scheduled for

Week 10 of protocol treatment, the first post-chemoradiotherapy dose of pembrolizumab may be DELAYED up to 3 weeks to allow for recovery from acute toxicities, in accordance with the treating investigator's judgment. In the case of such delay, the following three doses of pembrolizumab will then be scheduled every 3 weeks (+/- 3 days) from the first post-chemoradiotherapy dose.

Subjects should receive appropriate supportive care measures as deemed necessary by the treating investigator. Suggested supportive care measures for the management of adverse events with potential immunologic etiology are outlined in Table 4 below and in greater detail below. Where appropriate, these guidelines include the use of oral or intravenous treatment with corticosteroids as well as additional anti-inflammatory agents if symptoms do not improve with administration of corticosteroids. Note that several courses of steroid tapering may be necessary as symptoms may worsen when the steroid dose is decreased. For each disorder, attempts should be made to rule out other causes such as metastatic disease or bacterial or viral infection, which might require additional supportive care. The treatment guidelines are intended to be applied when the investigator determines the events to be related to pembrolizumab.

Note: if after the evaluation the event is determined not to be related to pembrolizumab, the investigator is instructed to follow the Events of Clinical Interest (ECI) reporting guidance but does not need to follow the treatment guidance (as outlined in the ECI guidance document). Please see section 12.4.2 for ECI reporting guidance.

It may be necessary to perform conditional procedures such as bronchoscopy, endoscopy, or skin photography as part of evaluation of the event. Suggested conditional procedures, as appropriate, can be found in the ECI guidance document.

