Table 4. Pembrolizumab Dose Modification Guidelines for Drug-Related Adverse Events

Toxicity	Hold Pembrolizumab For NCI CTCAE Grade	Timing for Restarting Treatment	Discontinue Pembrolizumab Permanently
Out-of-field Rash (skin rash outside of the radiation field)	3	Toxicity resolves to Grade 0-1 and the patient has tapered off of or did not require systemic corticosteroids. (Ongoing management with topical steroids is acceptable.)	Toxicity does not resolve within 12 weeks of last dose or inability to taper off of corticosteroids within 12 weeks.
In-field radiation dermatitis (skin rash within the radiation field) – Arm 2	4 ^a	Toxicity resolves to Grade 3 or less. NOTE: systemic and topical steroids should be avoided in the case of radiation dermatitis that is restricted to in-field.	Toxicity does not resolve to Grade 3 or better within 6 weeks of completing IMRT
Diarrhea/Colitis	2-3	Toxicity resolves to Grade 0-1 and the patient has successfully tapered off of corticosteroids.	Toxicity does not resolve within 12 weeks of last dose or inability to taper off of corticosteroids within 12 weeks.
	4	Permanently discontinue	Permanently discontinue
AST, ALT, or Increased Bilirubin	2	Toxicity resolves to Grade 0-1 and the patient has tapered off of corticosteroids.	Toxicity does not resolve within 12 weeks of last dose.
	3-4	Permanently discontinue	Permanently discontinue

Toxicity	Hold Pembrolizumab For NCI CTCAE Grade	Timing for Restarting Treatment	Discontinue Pembrolizumab Permanently
Type 1 diabetes mellitus (if new onset) or Hyperglycemia	T1DM or 3-4	Hold pembrolizumab for new onset Type 1 diabetes mellitus or Grade 3-4 hyperglycemia associated with evidence of beta cell failure.	Resume pembrolizumab when patients are clinically and metabolically stable.
Hypophysitis	2-3	Toxicity resolves to Grade 0-1	Toxicity does not resolve within 12 weeks of last dose or inability to taper corticosteroids to a dose of prednisone 10 mg or less within 12 weeks.
	4	Permanently discontinue	Permanently discontinue
Hyperthyroidism	3	Toxicity resolves to Grade 0-1	Toxicity does not resolve within 12 weeks of last dose or inability to taper off corticosteroids within 12 weeks.
	4	Permanently discontinue	Permanently discontinue
Hypothyroidism	2-4	Therapy with pembrolizumab can be continued while treatment for the thyroid disorder is instituted	Therapy with pembrolizumab can be continued while treatment for the thyroid disorder is instituted.

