 - For **Grade 2 events**, treat with systemic corticosteroids. When symptoms improve to Grade 1 or less, steroid taper should be started and continued over no less than 4 weeks.
 - For **Grade 3-4 events**, immediately treat with intravenous steroids. Administer additional anti-inflammatory measures, as needed.
 - Add prophylactic antibiotics for opportunistic infections in the case of prolonged steroid administration.

- **Diarrhea/Colitis:**

Subjects should be carefully monitored for signs and symptoms of enterocolitis (such as diarrhea, abdominal pain, blood or mucus in stool, with or without fever) and of bowel perforation (such as peritoneal signs and ileus).

- All subjects who experience diarrhea/colitis should be advised to drink liberal quantities of clear fluids (or to administer liberal quantities of clear fluids via PEG tube if present). If sufficient oral or PEG-tube fluid intake is not feasible, fluid and electrolytes should be substituted via IV infusion. For Grade 2 or higher diarrhea, consider GI consultation and endoscopy to confirm or rule out colitis.
- For **Grade 2 diarrhea/colitis** that persists greater than 3 days, administer oral corticosteroids.
- For **Grade 3 or 4 diarrhea/colitis** that persists > 1 week, treat with intravenous steroids followed by high dose oral steroids.
- When symptoms improve to Grade 1 or less, steroid taper should be started and continued over no less than 4 weeks.

- **Type 1 diabetes mellitus (if new onset, including diabetic ketoacidosis [DKA]) or ≥ Grade 3 Hyperglycemia, if associated with ketosis (ketonuria) or metabolic acidosis (DKA):**

- For **T1DM or Grade 3 – 4 Hyperglycemia:**
 - Insulin replacement therapy is recommended for Type I diabetes mellitus and for Grade 3-4 hyperglycemia associated with metabolic acidosis or ketonuria.
 - Evaluate patients with serum glucose and a metabolic panel, urine ketones, glycosylated hemoglobin, and C-peptide.

- **Hypophysitis:**

- For **Grade 2** events, treat with corticosteroids. When symptoms improve to Grade 1 or less, steroid taper should be started and continued over no less than 4 weeks. Replacement of appropriate hormones may be required as the steroid dose is tapered.

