5.7.1 DLT

DLT is defined as the occurrence of a severe adverse event (AE) listed below that is *at least possibly* related to pembrolizumab and occurs within 24 weeks of the initiation of pembrolizumab on either treatment arm. AEs will be graded according to NCI CTCAE version 4.0.

DLT Definition:

Since autoimmune/inflammatory events may occur at any time during the course of treatment, and may occur with evidence of clinical benefit, the following criteria will be used to define DLT:

- Any \geq Grade 4 non-hematologic toxicity **except**:
 - Grade 4 in-field radiation dermatitis for which IMRT is held \leq 1 week (5 fractions).
 - Grade 4 mucositis for which IMRT is held \leq 1 week (5 fractions).
 - Asymptomatic Grade 4 hypomagnesemia or hypokalemia, which corrects to Grade \leq 2 with replacement therapy.
- An alanine or aspartate amino transaminase elevation of greater than three times the upper limit of normal with concurrent elevation of bilirubin two times the upper limit of normal attributable to pembrolizumab should be considered a DLT. Patients meeting this criterion should be permanently discontinued from pembrolizumab.
- Autoimmune toxicity of any grade requiring systemic corticosteroids or other anti-inflammatory that cannot be tapered off in less than 12 weeks.
- Delay in completion of radiation therapy >10 fractions, or inability to complete prescribed IMRT course, due to immune toxicity at least possibly attributed to pembrolizumab.
- Grade ≥ 3 neutropenia with fever (oral temperature $> 39^{\circ}\text{C}$).
- Grade ≥ 3 thrombocytopenia with bleeding.

Patients who experience a DLT will receive no additional doses of pembrolizumab and will be withdrawn from the protocol. Patients may complete cisplatin and radiation per standard of care.

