9. STATISTICAL METHODS

This is a randomized, parallel group, non-comparative phase II trial evaluating the safety and efficacy of two schedules of fixed-dose pembrolizumab combined with standard cisplatin-IMRT in intermediate or high risk, PULA HNSCC: sequential and concurrent. This study is being performed in order to provide: a) necessary safety experience; b) preliminary efficacy estimates; c) characterization of the PD-L1 biomarker in the context of definitive chemoradiation; d) the recommended schedule for definitive testing.

Primary Objective

To evaluate two schedules of fixed-dose pembrolizumab (concurrent vs. sequential) added to standard, concurrent cisplatin-IMRT in patients with PULA HNSCC, in order to recommend the schedule to be tested in a subsequent definitive, randomized study.

Sample Size Determination

The target sample size is 40 evaluable patients per arm. Assuming 10% drop out or ineligibility, 90 patients will be randomized (all evaluable patients will be analyzed). The sample size is determined based upon the following assumptions: 1) the 1-year PFS in the high risk population treated with conventional cisplatin-radiotherapy is 60%;⁶ 2) As defined, DLTs occurring in more than 20% of the study population are unacceptable and would constitute an unsafe regimen; 3) The study requires adequate power to detect a signal of antagonism, defined as a 1-year local failure rate

[figure not shown]
exceeding 60%. To advance to Phase II/III testing, a treatment arm must meet all of the following criteria:

- DLT occurs in $\leq 20\%$
- 1-year local failure rate is $< 60\%$
- 1-year PFS is $\geq 60\%$

If both arms meet the above criteria, then the treatment arm demonstrating numerically superior 1-year PFS will advance for definitive testing, as in a so-called “pick-the-winner” trial model. An early phase trial cannot provide the statistical power required for a formal statistical comparison between arms.

The graphic in Figure 1 below demonstrates the probability of accepting either treatment (that is, based on $n = 40$ evaluable patients per arm) by means of 90% one-sided exact confidence intervals (CI) for DLT, 1-year failure rate, and 1-year PFS. If the upper bound of the DLT CI is less than 0.20, the upper bound of the failure CI is less than 0.60, and the lower bound of the 1-year PFS CI is greater than 0.60, the treatment will be accepted.

Figure 1: Probability of accepting the treatment according to the three primary metrics

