Early Stopping Rule

Dose Limiting Toxicity (DLT; see Section 5.8 for DLT definition) will be continuously monitored in both treatment arms, and is explicitly intended for the purposes of safety monitoring of the concurrent combination of pembrolizumab and cisplatin-IMRT (Arm 2). As defined, excess DLT is not expected during standard of care cisplatin-IMRT. Excess DLT in either arm, however, would trigger the early stopping rule. A continuous Bayesian stopping rule will be adopted, once 4 patients have accrued to either treatment arm. For either arm, if $p(p(DLT) > 0.2) \geq 0.6$, then the stopping rule would be triggered. Table 11 describes the number of DLTs per number of treated patients required to trigger the early stopping rule, which will require a suspension of accrual to that Arm and evaluation of toxicity data by the H&N Program DSMC to determine further action.

Table 11. Boundaries for the Early Stopping Rule for Excess DLT

	Number of patients treated on that Arm
--	--

	4	8	12	16	20	24	28	32	36
Accrual to the arm is halted if the number of DLTs is greater than or equal to	2	3	4	4	5	6	7	8	9

Analysis Plan

The proportions of patients experiencing DLT, local failure at 1 year, or are progression-free at one year will be calculated with exact (Klopper-Pearson) 90% confidence intervals. Adverse events will be tabulated by category and grade. The relationship between the three primary metrics and baseline PD-L1 expression will be assessed using logistic regression.

Secondary Endpoints

Toxicity

All patients will be evaluable for toxicity from the time of their first treatment with pembrolizumab. The proportion of DLTs in each dosing arm (concurrent vs. sequential) will be reported, as will the proportion of AEs in accordance with NCI CTCAE v.4 grading criteria.

Preliminary efficacy data

Overall and progression-free survival in both arms will be characterized by product-limit (Kaplan-Meier) survival function estimates with appropriate confidence intervals. The study is not adequately powered for a formal test comparing PFS between arms.

10. LABELING, PACKAGING, STORAGE AND RETURN OF CLINICAL SUPPLIES 10.1Investigational Product

The investigator shall take responsibility for and shall take all steps to maintain appropriate records and ensure appropriate supply, storage, handling, distribution and usage of the investigational product, pembrolizumab, in accordance with the protocol and any applicable laws and regulations.

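### For resolved Grade 2-3 hypophysitis still on prednisone 10 mg or less at 12 weeks, Table 4 with 5.3.1 directs further pembrolizumab while 5.7.1 withdraws the patient as a DLT (minor)

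*Combined protocol and SAP*

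**What the plan says.** Three places in the combined protocol and SAP bear on this.

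- **Section 5.3.1, Table 4, hypophysitis Grade 2-3.** Pembrolizumab is held and may restart once the toxicity is back to Grade 0-1. The row does not require steroids to have stopped. Permanent discontinuation follows if the toxicity has not resolved within 12 weeks of the last dose, or for "inability to taper corticosteroids to a dose of prednisone 10 mg or less within 12 weeks".
- **Section 5.3.1, text.** "If the subject meets retreatment criteria, the full dose of 200 mg will be administered." Hypophysitis is treated with corticosteroids: "When symptoms improve to Grade 1 or less, steroid taper should be started and continued over no less than 4 weeks." Hormone replacement may be needed as the steroid dose comes down.
- **Section 5.7.1.** A DLT must have at least a possible link to pembrolizumab and be one that "occurs within 24 weeks of the initiation of pembrolizumab on either treatment arm". One listed criterion is "Autoimmune toxicity of any grade requiring systemic corticosteroids or other anti-inflammatory that cannot be tapered off in less than 12 weeks". The consequence is stated flatly: "Patients who experience a DLT will receive no additional doses of pembrolizumab and will be withdrawn from the protocol."

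Neither section refers to the other on this point, and no text gives an order of precedence.

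**The concern.** Table 4 tolerates a low steroid dose at 12 weeks after hypophysitis, and 5.7.1 tolerates none. For a patient between those two limits, a site that works from the dosing table gives the next 200 mg dose, and a site that works from the DLT section stops the drug and withdraws the patient. Both sites would be following the protocol. What is at stake is consistent handling of an immune-related safety event across sites and arms, for the doses that fall due at or after the 12-week mark.

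**Working it through.** **1. The two rules side by side**

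| | Table 4 with 5.3.1 | 5.7.1 |
|---|---|---|
| Event | Drug-related hypophysitis, Grade 2-3 | Autoimmune toxicity, any grade, possibly related or more |
| Steroid limit at 12 weeks | Prednisone 10 mg or less is acceptable | Must be fully off in less than 12 weeks |
| Below the limit | Full 200 mg dose is given | Not a DLT on this criterion |
| Above the limit | Stop pembrolizumab | DLT: stop pembrolizumab and withdraw |

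The rules disagree only where the steroid dose at 12 weeks is above zero but no more than prednisone 10 mg, with the toxicity already at Grade 0-1. The lead-in to 5.7.1 speaks of severe events, but the criterion itself covers every grade, so Grade 2 is included. The other Table 4 rows that set a 12-week steroid limit (out-of-field rash, diarrhea/colitis, hyperthyroidism, pneumonitis, renal, all other) require tapering fully off, which agrees with 5.7.1. Hypophysitis is the exception.

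**2. Can protocol-compliant care produce such a patient?** The taper starts at Grade 1 or less and lasts at least 4 weeks. If Grade 1 is reached at week 8, the earliest week off steroid is 8 + 4 = 12, which is not less than 12. The patient can nevertheless be at 10 mg or less by then. So the case can occur. This counts weeks from steroid start, which is an assumption because 5.7.1 gives no starting point for its 12 weeks.

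**3. How many doses are affected?** The 8 doses fall at t = 0, 3, 6, 9, 12, 15, 18 and 21 weeks after the first. For Arm 1 this takes week 27 from Appendix C, where Table 2 prints week 25. With steroid started at week s after the first dose, the disputed doses are those with t ≥ s + 12.

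| Steroid start s | Cut-off s + 12 | Doses left, usual schedule | Doses left, Arm 2 delayed 3 weeks |
|---|---|---|---|
| 3 | 15 | 3 | 4 |
| 6 | 18 | 2 | 3 |
| 9 | 21 | 1 | 2 |
| 12 | 24 | 0 | 1 |

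The last column uses t = 0, 3, 6, 12, 15, 18, 21 and 24, since Section 5 lets the week 9 dose slip by up to 3 weeks and moves later doses with it. In Arm 1 that delay moves the first dose, so the spacing does not change. If the 12 weeks ran from the last dose given instead, 4, 3, 2 or 1 doses would remain on the usual schedule after dose 1, 2, 3 or 4.

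**4. Is the case inside the DLT window?** If the DLT is dated at the 12-week mark, it needs s + 12 ≤ 24, so s ≤ 12. Every row in the table meets that.

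**5. Does the DLT count become uncertain?** Section 9 uses DLTs in the acceptance rule ("If the upper bound of the DLT CI is less than 0.20") and in Table 11 ("Accrual to the arm is halted if the number of DLTs is greater than or equal to"). With n = 40, the one-sided 90% exact upper bound is the 0.90 quantile of Beta(x + 1, 40 − x). It is 0.190 for x = 4 (pass) and 0.220 for x = 5 (fail), so one patient can decide an arm that sits at the boundary. But whether a patient is a DLT is settled by 5.7.1 alone. Table 4 plays no part in the count.

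**The case against.** The best reply is that the rules are layered. Table 4 is a set of guidelines for holding and restarting, 5.7.1 is an absolute stop placed over it, and a withdrawn patient is no longer subject to retreatment criteria. That is probably the intended order. It is not written anywhere, 5.3.1 says without qualification that the dose will be given, and the reading leaves the 10 mg allowance with no effect at 12 weeks inside the DLT window.

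A second reply concerns timing. In the week 8 example, Table 4 permits restart at week 8, before the 12-week steroid criterion has been reached. This is correct, and it confines the conflict to doses from the 12-week mark on.

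A third reply is that low-dose steroid after resolved hypophysitis is hormone replacement, not treatment, which would explain why only this row has an allowance. That is plausible and would remove part of the conflict. But 5.7.1 does not exempt replacement, Table 4 describes the 10 mg as a taper level, and patients still tapering therapeutic steroid would remain in conflict. The minimum 4-week taper does not set hypophysitis apart, since pneumonitis, colitis, hepatic and renal events have it too. The 10 mg allowance does.

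A reader might also infer that the contradiction disturbs the DLT acceptance rule and the stopping boundaries. With other DLTs assumed at 10% and these cases assumed at 0.5%, 1% or 2%, the chance of at most 4 DLTs in 40 falls from 63% to 59%, 55% or 47%. Those figures compare 5.7.1 as written with a looser definition, at rates the documents do not give. The same holds for any shift in Table 11 crossing probabilities. They do not measure the conflict with Table 4.

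**Conclusion.** Wrong as written, and minor. For pembrolizumab-related Grade 2-3 hypophysitis that has resolved to Grade 0-1 but still needs steroid at prednisone 10 mg or less at 12 weeks, inside the 24-week window, two sections give opposite dosing instructions and nothing ranks them.

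The size is inconsistent dosing over about 0 to 3 remaining doses, up to 4 in a delayed Arm 2, in a patient who is likely to be rare. This rests on counting the 12 weeks from steroid start, on the planned 3-week spacing, and on low-dose steroid counting as steroid not tapered off.

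The documents do not support two stronger readings. The first is that Table 4 makes the DLT total ambiguous: it does not, because 5.7.1 is the only definition. The one open term is hormone replacement, and that is a gap inside 5.7.1. The second is that the DLT criterion is mistaken and must be relaxed to 10 mg. How strict a DLT should be is the sponsor's choice.

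**What to change.** Three wording changes.

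1. In Table 4, Grade 2-3 hypophysitis, change the steroid part of the discontinuation criterion to: *inability to taper off corticosteroids in less than 12 weeks*.
2. Add a note to Table 4: *a patient who meets a DLT criterion in Section 5.7.1 receives no further pembrolizumab, whatever this table allows*.
3. State in 5.7.1 whether physiologic hormone replacement counts as steroid not tapered off, for both arms alike.

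This needs no new visits, tests or patients. The downside is that a few patients on low-dose steroid lose their remaining doses, which 5.7.1 already requires. The sponsor could instead write the 10 mg allowance into 5.7.1. That also removes the conflict, but it loosens a safety criterion for one event type and should be adopted only as a deliberate decision.

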Infusion Reaction	3-4	Permanently discontinue	Permanently discontinue
Pneumonitis	2	Toxicity resolves to Grade 0-1	Toxicity does not resolve within 12 weeks of last dose or inability taper off corticosteroid within 12 weeks.
	3-4	Permanently discontinue	Permanently discontinue
Renal Failure or Nephritis ^b – Serum/Whole Creatinine	2 ^c	Toxicity resolves to Grade 0-1	Toxicity does not resolve within 12 weeks of last dose or inability to taper off corticosteroid within 12 weeks.
	3-4	Permanently discontinue	Permanently discontinue
All Other Drug-Related Toxicity ^d	3 or Severe	Toxicity resolves to Grade 0-1	Toxicity does not resolve within 12 weeks of last dose or inability taper off of corticosteroids within 12 weeks.
	4	Permanently discontinue	Permanently discontinue

Note: Permanently discontinue pembrolizumab for any severe or Grade 3 drug-related AE that recurs or any life-threatening event.

^a Per investigator discretion, pembrolizumab may be held for grade 3 in-field radiation dermatitis. If pembrolizumab is held for grade 3 in-field radiation dermatitis, no specific grade of resolution is required to restart pembrolizumab; restart would also be per investigator discretion.

^b NOTE: Dose modification of cisplatin in the setting of renal insufficiency is addressed separately in Section 5.3.2.

^c NOTE: if event is considered **clinically unrelated or unlikely to be related to pembrolizumab**, and an alternate clinical explanation is likely, probable, or definite in the judgment of the investigator (example, attributable to cisplatin and/or prerenal azotemia in the setting of nausea, and responding to hydration), then corticosteroids may be omitted and pembrolizumab may be administered.

^d Patients with intolerable or persistent Grade 2 drug-related AE may hold pembrolizumab at physician discretion. Permanently discontinue pembrolizumab for persistent Grade 2 adverse reactions for which treatment with study drug has been held, and that do not recover to Grade 0-1 within 12 weeks of the last dose of pembrolizumab. Note: Pembrolizumab does **not** need to be held for grade 3 dysphagia, grade 3 pain, grade 3 weight loss, or grade 3 fatigue, which are expected toxicities for chemoradiation of HNSCC and will be managed aggressively by treating investigators per standards of care.

- **Pneumonitis:**

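### Table 4 and Section 5.7.1 give incompatible instructions on further pembrolizumab for a narrow set of severe, possibly related events

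*Combined protocol and SAP*

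**What the plan says.** Section 5.7.1 applies to events at least possibly related to pembrolizumab that occur within 24 weeks of its first dose, in either arm. Its first criterion covers "Grade 4 non-hematologic toxicity" and anything more severe, with three exceptions. One is "Grade 4 in-field radiation dermatitis for which IMRT is held" for no more than one week (5 fractions). The others are mucositis with the same limit, and asymptomatic low magnesium or potassium that corrects with replacement. A later criterion is "Autoimmune toxicity of any grade requiring systemic corticosteroids or other anti-inflammatory that cannot be tapered off in less than 12 weeks". Grade 3 or higher neutropenia with fever, and grade 3 or higher thrombocytopenia with bleeding, are also DLTs. The consequence is the same for every type of event: "Patients who experience a DLT will receive no additional doses of pembrolizumab and will be withdrawn from the protocol".

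Table 4 in Section 5.3.1 sets the dose action for drug-related events row by row:

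- Hypothyroidism, grade 2-4: "Therapy with pembrolizumab can be continued while treatment for the thyroid disorder is instituted".
- New-onset type 1 diabetes, or grade 3-4 hyperglycemia with beta cell failure: hold, then "Resume pembrolizumab when patients are clinically and metabolically stable".
- In-field dermatitis in Arm 2, grade 4: restart once at grade 3 or less. The permanent stop applies only if that grade is not reached within 6 weeks of finishing IMRT.
- Hypophysitis, grade 2-3: one ground for a permanent stop is "inability to taper corticosteroids to a dose of prednisone 10 mg or less within 12 weeks".

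The Note below the table reads: "Permanently discontinue pembrolizumab for any severe or Grade 3 drug-related AE that recurs or any life-threatening event". The text of Section 5.3.1 adds that the full 200 mg is to be given when retreatment criteria are met. Table 13 (Section 12.4.3) describes grade 4 as having life-threatening consequences.

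**The concern.** Both sections govern the same patients: those with a severe event that may be due to pembrolizumab. For a few events one section ends pembrolizumab and removes the patient from the protocol, while the other allows or directs further doses. Table 4 does not mention DLTs, Section 5.7.1 does not mention Table 4, and neither is given precedence. Two sites could therefore handle the same event differently, one re-dosing the patient and the other withdrawing the patient. The question is whether a patient receives the investigational drug again after a severe reaction, so this is first a patient-safety matter. It also makes exposure and withdrawal depend on which section a site happens to follow. The dermatitis row applies only to Arm 2, the arm whose safety Section 5.7 says DLT monitoring is chiefly meant to watch.

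**Working it through.** No figure in the plan depends on this point, so the check is a comparison of texts plus one piece of arithmetic on timing.

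**1. Could the two rules apply at different times?** The DLT window is 24 weeks from the first pembrolizumab dose. The dosing weeks come from Tables 2 and 3 in Section 5.

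- Arm 1: week 9 to week 30, so 30 - 9 = 21 weeks. Delaying the week 9 dose moves the first dose as well, so the span stays at 21.
- Arm 2: week -1 to week 21. Taking week -1 as one week before week 1, with no week 0, the span is (21 - 1) + 1 = 21 weeks. With the permitted 3-week delay of the week 9 dose it is 21 + 3 = 24 weeks.

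At the scheduled intervals, essentially every decision to re-treat falls inside the DLT window. Timing does not separate the rules.

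**2. Direct conflicts** (each for an event at least possibly related to pembrolizumab)

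| Event | Table 4 | Section 5.7.1 |
|---|---|---|
| Grade 4 hypothyroidism | May continue | DLT (not an exception): no more doses, withdrawn |
| Grade 4 hyperglycemia with beta cell failure | Hold, then resume when stable | DLT (not an exception): no more doses, withdrawn |
| Grade 4 in-field dermatitis, Arm 2, IMRT held more than 5 fractions | Restart at grade 3 or less, whatever the length of the hold | DLT (beyond the exception): no more doses, withdrawn |

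Dermatitis with IMRT held 5 fractions or fewer is not a DLT, so there is no conflict there. Section 5.4.12 withholds pembrolizumab during a radiotherapy break, but does not settle whether it may restart afterwards.

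**3. Does the Note resolve this?** Read with Table 13, the Note would stop pembrolizumab after any grade 4 event. The three rows above include grade 4 and do not stop it. The Note therefore sets Table 4 against itself.

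**4. Two mismatches of a weaker kind**

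- *Hypophysitis, grade 2-3.* Table 4 accepts steroids reduced to a low dose by 12 weeks; Section 5.7.1 asks that they be off in less than 12 weeks. A patient still on prednisone 10 mg or less at 12 weeks meets the first limit and appears to fail the second.
- *First grade 3 neutropenia with fever, or grade 3 thrombocytopenia with bleeding.* Both are DLTs. Table 4 has no row for either, so the catch-all row for other drug-related toxicity appears to apply: hold at grade 3, restart at grade 0-1. The Note reaches a grade 3 event only if it recurs, and Table 13 describes grade 3 as not immediately life-threatening.

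**5. Rows that agree.** Table 4 permanently stops pembrolizumab for grade 4 colitis, hypophysitis, hyperthyroidism and other drug-related toxicity, and for grade 3-4 hepatic events, pneumonitis, renal events and infusion reactions. That is eight rows with no grade 4 conflict. The out-of-field rash row gives no grade 4 instruction, which leaves the Note, and the Note agrees with Section 5.7.1. The hepatic grade 2 row was not compared with the DLT criterion on transaminases and bilirubin, because the CTCAE cut-offs are not in the documents.

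**The case against.** The best defence is that a stricter reading is available. Table 4 is titled as guidelines, Section 5.7.1 is categorical, and the Note puts a stop instruction in front of anyone using the table. The hypothyroidism row only permits continuation, so a site that stops complies with both sections. This would work if the plan said that Section 5.7.1 prevails, but it does not. The hyperglycemia row tells the site to resume, and Section 5.3.1 says the full dose will be given once retreatment criteria are met.

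Attribution also narrows the problem. Section 5.3.1 describes hypothyroidism as a common result of chemoradiotherapy, and in-field dermatitis is by name a radiation effect. Many such events may be judged unrelated. That limits how often the conflict arises. It does not remove it, because the DLT threshold is only possible relatedness.

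The hypophysitis case is open to argument. Table 4 there omits a mandatory stop rather than ordering a restart against one. The guidance in Section 5.3.1 expects hormone replacement as steroids are tapered, and does not say whether residual low-dose prednisone is replacement or a failed taper. If the 12-week failure must itself fall inside the 24-week window, only cases whose steroid course starts within 24 - 12 = 12 weeks of the first dose qualify. It is a mismatch of limits, not an opposite instruction.

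A reader might also infer that the conflict corrupts the DLT count, and with it the stopping and advancement decisions. The documents do not support this. Section 5.7.1 defines a DLT by event, attribution and timing, whatever dose action follows. Life-threatening events also go to the sponsor as serious adverse events within 24 hours, and safety is reviewed monthly. That sites would fail to flag a DLT is conjecture. It is true that one event can cross a boundary in Table 11 (2 of 4, 3 of 8, 4 of 12), but that holds for any rule based on counts. Nor is 8/40 (20.0%) against 9/40 (22.5%) decisive by itself. The Sample Size Determination text also requires the upper bound of a one-sided 90% exact interval to be below 0.20. That is met at 4/40 (bound 0.190) and not at 5/40 (0.220), so both 8/40 and 9/40 fail it.

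**Conclusion.** The inconsistency is real and limited. Three events carry incompatible instructions on further pembrolizumab, the Note conflicts with the same three rows, and two other provisions do not line up with Section 5.7.1. This assumes that the events are at least possibly related to pembrolizumab, fall within 24 weeks of the first dose and, for dermatitis, involve an IMRT hold of more than 5 fractions. The neutropenia and thrombocytopenia mismatch also assumes that the catch-all row covers hematologic events. The documents give no rates for these events, so the number of patients affected cannot be estimated.

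It would be wrong to read this as Table 4 contradicting the DLT rule throughout, since most of its other grade 4 instructions agree. No sample size, error rate or boundary changes. The point still needs correcting before use, because it concerns re-exposure to the investigational drug after severe toxicity and the plan offers no way to decide between its two answers.

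**What to change.** Reconcile the text of Section 5.3.1, Table 4 and its Note with Section 5.7.1, so that each of these has a single instruction on further pembrolizumab and on withdrawal:

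- grade 4 hypothyroidism;
- grade 4 hyperglycemia with beta cell failure;
- grade 4 in-field dermatitis in Arm 2 with IMRT held more than 5 fractions;
- hypophysitis with low-dose steroids remaining at 12 weeks;
- a first grade 3 neutropenia with fever, or grade 3 thrombocytopenia with bleeding.

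Which instruction applies is for the sponsor to decide; this review takes no position. State in both sections which one prevails if they differ. Marking in Table 4 the rows and grades that are DLTs, and saying that DLT status is assigned from Section 5.7.1 alone, would help but is optional. The cost is a protocol amendment to wording, with no added procedures, visits or patients.
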